#### **7.2.4 Timing of Dose Administration and Dose Delays**

Trial treatment should be administered on Day 1 of each cycle after all procedures and assessments have been completed as detailed on the Trial Flow Chart (Section 8.0). Pembrolizumab may be administered up to 3 days before or after the scheduled Day 1 of each cycle for administrative reasons. Participants should be placed back on pembrolizumab therapy within 3 weeks of the scheduled interruption, unless otherwise discussed with the Sponsor-Investigator. Dose delays in pembrolizumab administration will not affect timing or administration of radiation therapy. Dose delays in radiation therapy will be managed per institutional guidelines/standard of care and will not affect timing or administration of pembrolizumab therapy.

### 7.2.5 Trial Blinding/Masking

This is an open-label trial. The Sponsor-Investigator, treating physicians, subject and clinic/study staff will all be aware of the treatment being administered.

### 7.2.6 Acceptable Concomitant Medications

All treatments that the investigator considers necessary for a subject's welfare may be administered at the discretion of the investigator in keeping with the community standards of medical care. All concomitant medication from time of consent through the last study visit (Wound Care Follow-Up visit) will be recorded on the electronic case report form (eCRF) including all prescription, over-the-counter (OTC), herbal supplements, and IV medications and fluids. If changes occur during the trial period, documentation of drug dosage, frequency, route, and date may also be included on the eCRF.

All concomitant medications received within 28 days before the first dose of trial treatment and through the Wound Care Follow-Up visit should be recorded and evaluated for SAEs and ECIs as defined in Section 9.4.

### 7.2.7 Prohibited Concomitant Medications

Subjects are prohibited from receiving the following therapies during the Screening and Treatment Phase (including retreatment for post-complete response relapse) of this trial:

- Antineoplastic systemic chemotherapy or biological therapy
- Immunotherapy not specified in this protocol
- Chemotherapy not specified in this protocol
- Investigational agents other than pembrolizumab
- Live or attenuated vaccines within 30 days before the first dose of trial intervention and while participating in the trial.
  - Note: Any licensed COVID-19 vaccine (including for Emergency Use) in a particular country is allowed in the study as long as they are mRNA vaccines, replication-incompetent adenoviral vaccines, or inactivated vaccines. These vaccines will be treated just as any other concomitant therapy.  
Investigational vaccines (i.e. those not licensed or approved for Emergency Use) are not allowed.
  - Examples of live vaccines include, but are not limited to, the following: measles, mumps, rubella, varicella/zoster, yellow fever, rabies, BCG, and typhoid vaccine.
- Systemic glucocorticoids except when used for the following purposes:
  - To modulate symptoms of an AE that is suspected to have an immunologic etiology
  - For the prevention of emesis
  - To premedicate for IV contrast allergies

- To treat asthma or COPD exacerbations (only short-term oral or IV use in doses >10 mg/day prednisone equivalent)
- For chronic systemic replacement not to exceed 10 mg/day prednisone equivalent
- Other glucocorticoid use except when used for the following purposes:
  - For topical use or ocular use
  - Intraarticular joint use
  - For inhalation in the management of asthma or chronic obstructive pulmonary disease

Subjects who, in the assessment by the investigator, require the use of any of the aforementioned treatments for clinical management should be removed from the trial. Subjects may receive other medications that the investigator deems to be medically necessary.

The Exclusion Criteria describes other medications which are prohibited in this trial in Section 7.1.2. Medications or vaccinations specifically prohibited in the exclusion criteria are not allowed during the ongoing trial. If there is a clinical indication for a specifically prohibited medication during the trial, discontinuation from trial therapy may be required. The Sponsor-Investigator will discuss any questions regarding this with the Merck Clinical team.

There are no prohibited therapies during the Follow-up Phase.

### **7.3 Rescue Medications & Supportive Care**

#### **7.3.1 Supportive Care Guidelines**

Subjects should receive appropriate supportive care measures per institutional standard as deemed necessary by the treating investigator. Supportive care guidelines for the management of adverse events with potential immunologic etiology are outlined along with the dose modification guidelines in Section 7.2.1.1.2, [Table 3].

#### **7.3.2 Radiation Related Toxicities**

The expected toxicities related to radiation therapy may vary in relation to the site of irradiation. The most commonly observed toxicities include fatigue (Grade 3), and skin toxicities (Grade 3) such as rash, color changes, burning, blistering, or desquamation. Skin toxicities should be managed by radiation-oncology staff utilizing standard of care protocols.

The radiation oncologist may list expected toxicities for a given radiation treatment prior to administration of radiation treatment in the subject's medical record. Strict prospective

quality assurance of all radiation plans will be performed prior to initiation of radiotherapy, per institutional standards, to minimize risk of serious toxicity.

Toxicities of radiation should be treated according to standard institutional practices, including the prescription of steroids, if appropriate. Subjects will continue treatment if steroids are used to treat radiation-associated toxicity.

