### 3.5 Radiation

Neoadjuvant radiation will be given as per standard of care at a subject's treating institution. Typically this will be 50 Gy, though a minimum of 45 Gy is required. Radiation will be delivered with conventional fraction sizes of 1.8-2.0 Gy daily into given over 5-6 weeks in daily fractions. However, a minimum of 25 fractions is required. Radiation protocols will be tailored to the specific subject's needs and may include a variety of techniques including 3-dimensional conformal external beam radiation therapy (3D CRT) or Intensity Modulated Radiation Therapy (IMRT).

While not typical, occasionally oral or topical steroids are used by some providers to minimize radiation-related toxicity as part of normal standard of care. This is allowed, however, subjects participating in this trial should not use these agents prophylactically. Topical steroids (1% hydrocortisone cream) may be used for grade 2 or higher radiation toxicity. Oral and intravenous steroids should only be used as described in Section 7.2. Other standard supportive care medications, including Non-Steroidal Anti-Inflammatory Drugs (NSAIDs), may be used at the discretion of the treating physician for radiation-related toxicity.

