## 7.5 Subject Replacement Strategy

Should any subjects fail to complete at least 2 doses of pembrolizumab and surgery, they will be replaced.

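### Sections 7.2.7 and 7.3.2 contradict each other on whether a subject given systemic steroids for radiation toxicity continues treatment or is removed from the trial

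*Combined protocol and SAP*

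**What the plan says.** Section 7.3.2 of the combined protocol and SAP deals with radiation toxicity: "Toxicities of radiation should be treated according to standard institutional practices, including the prescription of steroids, if appropriate". It then gives the consequence: "Subjects will continue treatment if steroids are used to treat radiation-associated toxicity". No route of administration is named.

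Section 7.2.7 lists treatments prohibited in the Screening and Treatment Phase, among them: "Systemic glucocorticoids except when used for the following purposes". Five purposes follow: an adverse event of suspected immunologic cause, prevention of emesis, premedication for contrast allergy, asthma or COPD exacerbation, and chronic replacement at a capped dose. The nearest to the present case reads "To modulate symptoms of an AE that is suspected to have an immunologic etiology". The section then says that subjects who, in the investigator's assessment, "require the use of any of the aforementioned treatments for clinical management should be removed from the trial".

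Section 3.5 notes that some providers occasionally use oral or topical steroids to limit radiation toxicity, and continues: "This is allowed, however, subjects participating in this trial should not use these agents prophylactically". Two sentences later it adds: "Oral and intravenous steroids should only be used as described in Section 7.2".

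Two sections govern replacement. Section 7.5 states: "Should any subjects fail to complete at least 2 doses of pembrolizumab and surgery, they will be replaced". Section 7.2.3 replaces anyone who does not reach surgery, whatever the reason.

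**The concern.** Two sections give opposite consequences for the same event. An investigator who prescribes an oral or intravenous steroid for a radiation reaction finds in 7.3.2 that the subject goes on with treatment, and in 7.2.7 that the subject should leave the trial. Nothing in the document says which section prevails.

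What is at stake is first who remains on trial treatment, and whether two investigators would handle like subjects alike. There is also a possible knock-on. Because replacement depends on doses received and on surgery, a subject removed under one reading may be replaced, while the same subject under the other reading stays among the 26 judged for complete necrosis.

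**Working it through.** The check is mainly textual.

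**Step 1. Side by side, for a systemic steroid given in the Treatment Phase for toxicity attributed to radiation.**

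| Section | Is use allowed? | Consequence stated |
|---|---|---|
| 7.3.2 | Yes, if appropriate under institutional practice | Treatment continues |
| 7.2.7 | No; not among the five excepted purposes | Removal from the trial |
| 3.5 | Oral use allowed other than as prophylaxis, then oral and IV use confined to 7.2 | None |

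Only 7.2.7 and 7.3.2 state a continue-or-remove consequence, and the two are opposite. Section 3.5 gives no consequence. It adds to the conflict by permitting oral use and then pointing to a section whose list of purposes leaves it out. The mandatory discontinuation reasons in 7.4 do not name use of a prohibited medicine, so they do not settle the matter.

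**Step 2. Where there is no conflict.** Topical steroids are permitted in both 3.5 and 7.2.7. A systemic steroid for an event of suspected immunologic cause falls under the first exception in 7.2.7. Section 7.2.7 also states that no therapy is prohibited in the Follow-up Phase.

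**Step 3. From removal to replacement.** Under section 8.1, pembrolizumab is given in Weeks 1, 4 and 7 and radiation starts in Week 2. Under 7.2.3, surgery comes at least 4 weeks after the later of the last radiation and the last pembrolizumab dose. Removal during radiation therefore always precedes surgery.

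- Removed between the start of radiation and the Week 4 dose: only one dose received, so replaced under 7.5.
- Removed after the Week 4 dose, no surgery: replaced under both 7.5 and 7.2.3.
- Removed after the Week 4 dose, with later standard-of-care surgery off trial: the documents do not say whether that surgery counts, so replacement is undetermined.

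**Step 4. Can an effect on the primary rule be derived?** Inputs from section 10.1: n = 26, reference rate 15%, target rate 40%, success at 7 or more, stated power 94.4%. Exact binomial:

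- Power = P(X ≥ 7 | n = 26, p = 0.40) = 0.9441, which reproduces the plan's figure.
- One-sided type I error = P(X ≥ 7 | n = 26, p = 0.15) = 0.0833.

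The contradiction changes neither number. Going further needs two quantities that the documents do not give: the fraction f removed and replaced, and the complete-necrosis rate r those subjects would have had. If the overall rate is 15% and n stays at 26, the rate among retained subjects is (0.15 − f × r) / (1 − f). The values of f and r below are assumptions chosen only to show the range.

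| f | r = 0: retained rate | P(X ≥ 7) | r = 30%: retained rate | P(X ≥ 7) |
|---|---|---|---|---|
| 5% | 0.15/0.95 = 0.1579 | 0.104 | 0.135/0.95 = 0.1421 | 0.066 |
| 10% | 0.15/0.90 = 0.1667 | 0.129 | 0.12/0.90 = 0.1333 | 0.049 |
| 20% | 0.15/0.80 = 0.1875 | 0.202 | 0.09/0.80 = 0.1125 | 0.022 |

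Against 0.083, the result moves up or down according to r. If r equals 15%, the retained rate stays at 15% and nothing moves. The documents do not say which case applies.

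**The case against.** The best reply is that 7.3.2 is the specific rule for radiation toxicity and 7.2.7 the general one, worded with should, so a sensible reader would follow 7.3.2. On that view the defect is a missing sixth exception. This has some force as a guess at intent. It does not settle the text: 3.5 is equally specific to radiation, and it sends oral and intravenous use to 7.2.

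A second reply is that 7.3.2 means topical steroids, since the skin reactions it names can be treated that way. It names no route, however. Topical use is already permitted elsewhere, and 3.5 expressly mentions oral steroids for this purpose. What stands is that the conflict is limited to systemic use.

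A third is that the immunologic exception will cover some events, because attribution may be uncertain when pembrolizumab and radiation are given together. That is fair, and it narrows the point. It does not reach toxicity that the investigator attributes to radiation.

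A fourth is rarity. Section 3.5 calls steroid use for this purpose not typical. Against that, 7.3.2 lists Grade 3 fatigue and skin toxicity among the commonest radiation toxicities. Neither statement supplies a rate.

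A reader might also infer that the conflict selects the primary denominator, by replacing the subjects who tolerate radiation worst. The documents do not support that as a finding. It requires a systemic steroid, no applicable exception, 7.2.7 followed in preference to 7.3.2, replacement actually triggered, and a link between toxicity and necrosis that is stated nowhere. Nor do the documents suggest that these subjects leave the safety analysis: the adverse event endpoint in 5.2 covers all subjects.

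**Conclusion.** The contradiction between 7.2.7 and 7.3.2 is in the current text, and the wording of 3.5 adds to it. It applies to oral or intravenous steroids given in the Treatment Phase for toxicity attributed to radiation, and to nothing wider. This rests on reading alone and is firm.

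Its numerical size cannot be stated. The number of subjects affected, the number replaced, and the direction of any shift in the 7-of-26 rule all depend on quantities absent from the documents; the table above shows only that the shift could go either way. The stated power of 94.4% is not in dispute. The reason to correct the text is that it gives opposite instructions on who stays on trial treatment, with a possible but undetermined consequence for replacement.

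**What to change.** Reconcile 3.5, 7.2.7 and 7.3.2 so that a single instruction covers both the use of systemic steroids for radiation toxicity and whether the subject then continues or is removed. Which rule to adopt is the sponsor's clinical decision, and no view is offered here.

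If the reconciled rule removes such subjects, 7.2.3, 7.5 and 10.1 should also say consistently whether they are replaced and whether later standard-of-care surgery counts toward the primary endpoint. A sentence in 10.1 alone, exempting only these subjects from replacement, would not do, because it would contradict 7.2.3 and 7.5 as they stand.

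The cost is a wording amendment to three sections and, if removal is chosen, matching sentences in three more places. The sample size and decision rule do not change.

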### **7.3.3 Contraception**

Pembrolizumab may have adverse effects on a fetus in utero. Furthermore, it is not known if pembrolizumab has transient adverse effects on the composition of sperm.

For this trial, male subjects will be considered to be of non-reproductive potential if they have azospermia (whether due to having had a vasectomy or due to an underlying medical condition).

Please refer to Appendix B: Women of Childbearing Potential Definitions and Methods of Contraception for further details regarding definitions of childbearing potential for women and appropriate methods of contraception while on study.

Subjects should be informed that taking the study medication may involve unknown risks to the fetus (unborn baby) if pregnancy were to occur during the study. In order to participate in the study subjects of childbearing potential must adhere to the contraception requirement described in Appendix B throughout the study period up to 120 days after the last dose of pembrolizumab. If there is any question that a subject of childbearing potential will not reliably comply with the requirements for contraception, that subject should not be entered into the study.

### **7.3.4 Use in Pregnancy**

If a subject or subject's partner inadvertently becomes pregnant while the subject receiving study treatment with pembrolizumab, the Sponsor-Investigator and Merck will immediately be made aware (within 24 hours for Sponsor-Investigator and within 2 business days for Merck), and the subject will immediately be removed from the study. If the subject or partner of subject becomes pregnant, there will be an additional consent form required (pregnancy or pregnant partner consent) to follow the pregnancy to outcome. The study team will contact the subject at least monthly and document the subject's status until the pregnancy has been completed or terminated. The outcome of the pregnancy and/or any related serious adverse events (e.g., death, abortion, congenital anomaly, or other disabling or life-threatening complication to the mother or newborn) will be reported within 24 hours to the Sponsor-Investigator and within 2 working days to Merck.

The Sponsor-Investigator will make every effort to obtain permission to follow the outcome of the pregnancy and report the condition of the fetus or newborn to Merck.

### 7.3.5 Use in Nursing Women

It is unknown whether pembrolizumab is excreted in human milk. Since many drugs are excreted in human milk, and because of the potential for serious adverse reactions in the nursing infant, subjects who are breast-feeding are not eligible for enrollment.

## 7.4 Subject Withdrawal/Discontinuation Criteria

Subjects may withdraw consent at any time for any reason or be removed from the trial at the discretion of the Sponsor-Investigator for any reason. In addition, a subject may be withdrawn by the Sub-Investigator or the Sponsor-Investigator if enrollment into the trial is inappropriate, the trial plan is violated, or for administrative and/or other safety reasons. When a subject discontinues/withdraws prior to 90 Day Follow-Up Visit, all applicable activities scheduled for the 90 Day Follow-Up visit should be performed at the time of discontinuation.

A subject will be considered withdrawn and no longer followed if they enroll onto hospice care.

A subject must be discontinued from the trial for any of the following reasons:

- The subject or legal representative (such as a parent or legal guardian) withdraws consent.
- Unacceptable adverse experiences as described in Section 7.2.1.1
- Intercurrent illness that prevents further administration of treatment
- Sponsor-Investigator's decision to withdraw the subject
- The subject has a confirmed positive serum pregnancy test
- Noncompliance with trial treatment or procedure requirements
- The subject is lost to follow-up
- Administrative reasons
- Subject progresses (clinically and/or radiologically) and is no longer a surgical candidate.

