### **3.3 Safety Monitoring on Study and Post-Treatment Follow-Up**

Enrollment will begin with a single cohort of three subject slots. No additional enrollment will be permitted until the first three subjects have completed a full treatment schedule (defined as C1D1 of pembrolizumab through the End of Treatment visit). This temporary pause and review of data is to ensure thorough safety monitoring of the first three subjects enrolled. The data will be reviewed to ensure that pembrolizumab in combination with radiation therapy does not increase the toxicity profile of either treatment in a manner that is unexpected or compromises subject safety.

During this initial 3-subject enrollment, if one or more of the three subjects experiences a serious unexpected adverse event at least possibly related to pembrolizumab or radiation treatment, the temporary enrollment hold will be extended as the Sponsor-Investigator evaluates the potential risk and safety. During this enrollment hold, the Sponsor-Investigator will review all currently collected safety data and make an evaluation as to whether to permit further accrual.

If none of the first three subjects experience a serious unexpected adverse event related to pembrolizumab or radiation treatment, enrollment may continue without restriction. If at any point in time there is greater than 30% of subjects who have unexpected, probably related SAEs grade III or higher that do not resolve to grade 2 within 2 weeks, the trial will pause enrollment for safety review by the Sponsor-Investigator.

All subjects will have an End of Treatment visit 30 days ( $\pm$  14 days) after the completion of pembrolizumab therapy, which may coincide with the pre-operative visit. Subjects will have a Wound Care Follow-Up visit 30 days ( $\pm$  14 days) after their first standard of care post-operative visit to determine how the wound healing is proceeding. If there are wound healing complications or any other ongoing toxicities related to treatment at that time, the subject will continue to be monitored until the toxicity/complication resolves, improves to maximal anticipated improvement, or the study closes.

Subjects will be followed for as many as 5 years after completing treatment for survival determination. This may be done via publicly available records, medical record review, or by phone.

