### 4.3 Exploratory Objectives

1. To make preliminary estimates of event-free survival and overall survival at one year.
2. To analyze changes occurring in tumor immune infiltrates following pembrolizumab and standard of care, neoadjuvant radiation, including but not limited to:
  - Number of CD4 and CD8 T cells
  - Phenotype of infiltrating T cells
  - Number of FoxP3 Regulatory T cells
  - Number of macrophages
  - Phenotype of Macrophages
  - Gene expression in immune infiltrates
  - For tumors with known immunogenic targets, the number and phenotype of antigen specific T cells
3. To determine volumetric size response and perform quantitative radiomic analysis.
4. To measure the time of wound healing following surgery and the rate of wound healing complications following definitive surgery.

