After the Wound Care Follow-Up Visit (or 90 Day Follow-Up Visit if the Wound Care Follow-Up visit is omitted), subjects will be contacted by telephone or medical record review every 12 weeks ( $\pm$  2 weeks) to assess for disease status, recurrence, and survival status until 1 year after initiation of pembrolizumab, death, withdrawal of consent, or the end of the study, whichever occurs first. After the first year, then subjects will be contacted via telephone or medical record review every 6 months ( $\pm$  2 months) to assess for disease status, recurrence, and survival status until 5 years after initiation of pembrolizumab, until death, withdrawal of consent, or the end of the study, whichever comes first.

Female subjects of child-bearing potential must have a negative serum pregnancy test at screening. Subsequent cycles may be either serum or urine tests. If more than 72 hours elapses between screening negative serum pregnancy assessment and C1D1, the negative serum pregnancy should be reconfirmed prior to administration of C1D1 treatment.

End of Treatment disease assessment via imaging must be completed within 3 weeks prior to planned surgery.

Archival tissue may be used instead of fresh biopsy collection. If archival tissue is utilized at baseline, tissue must have been collected within 90 days prior to planned Week 1 Day 1. End of treatment tissue will be collected from surgical resection. If no surgical resection occurs, this tissue will not be collected.

ECOG performance status must be confirmed within 7 days prior to the date of C1D1. If more than 7 days elapse between ECOG assessment and C1D1, the ECOG performance status should be reconfirmed prior to administration of C1D1 treatment.

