### **9.3.6 Survival Follow-up**

Disease status and any subsequent anticancer therapy information status will continue to be monitored. Subjects will be contacted by telephone or medical record review every 12 weeks ( $\pm$  2 weeks) after the 30 Day Follow-Up Visit to assess for disease status, recurrence, and survival status until 1 year after initiation of pembrolizumab therapy, death, withdrawal of consent, or the end of the study, whichever occurs first. After the first year, then subjects will be contacted either by telephone or medical record review every 6 months ( $\pm$  1 month) to assess for disease status, recurrence, and survival status until 5 years after initiation of pembrolizumab, death, withdrawal of consent, or the end of the study, whichever comes first.

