#### **9.4.2 Immediate Reporting of Adverse Events to the Sponsor and to Merck**

##### **9.4.2.1 Serious Adverse Events**

A serious adverse event is any adverse event occurring at any dose or during any use of Merck's product that:

- Results in death;
- Is life threatening;
- Results in persistent or significant disability/incapacity;
- Results in or prolongs an existing inpatient hospitalization;
- Is a congenital anomaly/birth defect;
- Is an other important medical event

**Note:** In addition to the above criteria, adverse events meeting either of the below criteria, although not serious per ICH definition, are reportable to Merck in the same timeframe as SAEs to meet certain local requirements. Therefore, these events are considered serious by Merck for collection purposes.

- Is a new cancer (that is not a condition of the study);
- Is associated with an overdose. For purposes of this study, an overdose of pembrolizumab will be defined as any dose of 1,000 mg or greater. No specific information is available on the treatment of overdose of pembrolizumab. In the event of overdose, the participant should be observed closely for signs of toxicity. Appropriate supportive treatment should be provided if clinically indicated.

For the time period beginning when the consent form is signed until treatment is started, any serious adverse event, including death due to any cause must be reported within 24 hours to the Sponsor-Investigator and within 2 working days to Merck Global Safety only if

it causes the subject to be excluded from the trial, or is the result of a protocol-specified intervention, including but not limited to washout or discontinuation of usual therapy, diet, placebo treatment or a procedure.

For the time period beginning at treatment initiation through 90 days following cessation of pembrolizumab or 30 days post following cessation of pembrolizumab if patient initiates a new anticancer therapy (whichever is earlier), any serious adverse event, including death due to any cause whether or not related to the Merck product, must be reported within 24 hours to the Sponsor-Investigator and within 2 working days to Merck Global Safety.

Additionally, any SAE brought to the attention of an investigator at any time outside of the time period specified above must be reported immediately to Merck if the event is considered drug related.

All subjects with serious adverse events must be followed up for outcome.

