## 10.0 STATISTICAL ANALYSIS PLAN

### 10.1 Statistical Analysis Plan Summary

The rationale for combining radiation and immunotherapy has been written about extensively . However, these studies have focused on hypofractionated radiation in the metastatic setting and none of these published studies have examined the use of Pembrolizumab with the neoadjuvant radiation schedules that are typically used in the curative setting for many malignancies. Safety will be evaluated by CTCAE 5.0 and tabulated for qualitative description.

With regards to efficacy analysis, RECIST evaluations will be performed and tabulated in both qualitative and quantitative formats. This is a pilot trial that is not powered to give definitive determination of efficacy. As RECIST partial responses are not typically seen following neoadjuvant radiation alone, any objective responses would be highly interesting and encouraging of further study either for soft-tissue sarcomas generally or for a specific subtype where a response was observed.

The rate of complete necrosis will also be analyzed. It is assumed that the rate of complete necrosis in this subject population is approximately 15% after chemoradiation . A design with 26 subjects has 94.4% power to detect an improvement in the complete necrosis rate from 15% to 40%. The observation of at least 7 subjects with complete necrosis would be considered evidence to rule out a 15% complete necrosis rate. With 26 subjects, binary proportions can be estimated to within 20%. Any toxicity with at least 10% prevalence has at least a 94% chance of being observed.

Event free survival and overall survival at 1 and 5 years will be determined in order to estimate the potential benefit in the highest risk subjects. We will generate Kaplan Meier curves to illustrate these overall survival rates and event-free survival rates. Using data already being analyzed under IRB approved protocols, we will compare these to historical controls at our institution using Cox's proportional hazard model. Subjects' demographic variables (such as age and gender) will be incorporated in the analysis.

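### Section 7.4 ends follow-up at hospice entry, while sections 8.1 and 9.3.6 continue it without a hospice exception; censoring there would bias the exploratory Kaplan-Meier OS upward

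*Combined protocol and SAP*

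**What the plan says.** Section 7.4, on withdrawal and discontinuation: "A subject will be considered withdrawn and no longer followed if they enroll onto hospice care". The sentence stands apart from the list of discontinuation reasons that follows it.

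Two other places set the end of survival follow-up. Section 8.1, Table 5 footnote 6, continues contact "until 5 years after initiation of pembrolizumab, until death, withdrawal of consent, or the end of the study, whichever comes first". Section 9.3.6 continues it "until 5 years after initiation of pembrolizumab, death, withdrawal of consent, or the end of the study, whichever comes first". Hospice is on neither list, and entering hospice is not withdrawal of consent.

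Section 3.3 sets a maximum of 5 years for survival follow-up and says how it may be obtained: "This may be done via publicly available records, medical record review, or by phone".

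Section 9.4.2.1 adds a safety route. From the start of treatment to 90 days after pembrolizumab stops (30 days if a new anticancer therapy starts), any serious event, "including death due to any cause whether or not related to the Merck product, must be reported within 24 hours" to the Sponsor-Investigator. It has no hospice exception either.

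Section 10.1 states that "Event free survival and overall survival at 1 and 5 years will be determined", plans Kaplan-Meier curves, and adds: "we will compare these to historical controls at our institution using Cox's proportional hazard model". It does not define OS or say when a subject is censored. Section 4.3 lists the aim as exploratory: "To make preliminary estimates of event-free survival and overall survival at one year".

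**The concern.** Kaplan-Meier assumes that a subject censored at a given time has the same later risk as those still followed. A subject who enters hospice does not: death is expected soon. If follow-up stops at that moment and the analyst censors there, the deaths most likely to occur next are removed from the event count.

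The resulting error has one direction. OS reads too high, and a larger sample would not cure it. Section 10.1 uses survival to judge potential benefit in the highest-risk subjects, who are plausibly the ones most likely to reach hospice. The practical risk is that site staff apply section 7.4 as written and no death date is collected for these subjects, which may be hard to recover later.

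**Working it through.** **Plan's own figure.** The plan gives no figure for OS or hospice use. Its only power figure belongs to the primary endpoint: 94.4% for at least 7 of 26, 15% against 40%. The exact binomial gives 94.41%, so it reproduces; nothing below depends on it.

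**Texts side by side.**
- Section 7.4: follow-up ends at hospice entry.
- Section 8.1 footnote 6 and section 9.3.6: follow-up ends at 5 years, death, withdrawal of consent or end of study.
- Section 3.3: a maximum duration and a permitted record route, so only in softer tension with 7.4.
- Section 10.1: no censoring rule to settle the matter.

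**Inputs for an illustration.**
- From the documents: 26 subjects (1.0, 10.1); third dose at Week 7 (Table 5), which is 42 days after the first; the 90-day and 30-day reporting limits (9.4.2.1).
- Assumed: exponential survival; 5-year OS, S5, of 50% or 70%; share h of deaths that follow hospice entry of 25%, 50% or 75%; every death inside the safety-reporting window is counted. Section 6.2.1.1 says about half of subjects with larger, higher-grade tumors develop fatal metastatic disease. That is a loose anchor, not a 5-year OS.

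**Formulas.**
- Hazard: λ = −ln(S5)/5, which is 0.1386 per year for 50% and 0.0713 for 70%.
- End of window: 42 + 90 = 132 days, so w = 132/365.25 = 0.361 years. With the 30-day limit: 42 + 30 = 72 days, w = 0.197.
- True survival: S(t) = exp(−λt).
- Survival that Kaplan-Meier would estimate, for t > w: KM(t) = exp(−λw) × exp(−λ(1−h)(t−w)).
- Standard error: √(S(1−S)/26).
- Deaths not recorded by 1 year: 26 × h × (S(w) − S(1)).

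**Results at 1 year, window to day 132.**

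| S5 | True 1-year OS | KM for h = 25 / 50 / 75% | Bias, points | Standard error, points |
|---|---|---|---|---|
| 50% | 0.871 | 0.890 / 0.910 / 0.930 | 1.9 / 3.9 / 6.0 | 6.6 |
| 70% | 0.931 | 0.942 / 0.953 / 0.964 | 1.1 / 2.1 / 3.2 | 5.0 |

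The bias is 0.21 to 0.91 standard errors. Expected deaths in year 1 are 26 × (1 − S(1)), or 1.8 to 3.4; of these, 0.28 to 1.57 would go unrecorded.

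A simulation with 26 subjects and hospice entry 30 or 60 days before death agrees with the formula to within 0.1 point (for S5 = 50%, h = 75%: 0.9303 and 0.9295 against 0.9303). The time from hospice to death therefore matters little.

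**Sensitivity.**
- Window to day 72 for everyone: 1-year bias 1.3 to 7.6 points (0.3 to 1.2 standard errors).
- No window: KM(t) = S(t)^(1−h), giving 1.7 to 9.5 points (0.3 to 1.5 standard errors).
- Weibull hazard, same 5-year OS, window to day 132: shape 1.5 gives 0.6 to 3.5 points; shape 0.8 gives 1.3 to 6.9.
- Two years, exponential, window to day 132: 2.6 to 14.1 points. Five years: 6.0 to 31.0 points.

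**Separate point on duration.** Section 1.0 estimates 12 months of enrollment in a 3-year trial. That leaves 3 − 1 = 2 to 3 − 0 = 3 years of follow-up per subject. A full 5 years for everyone needs about 1 + 5 = 6 years, yet section 10.1 plans 5-year estimates.

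**The case against.** The strongest reply is that the texts can coexist. The stopping lists in 8.1 and 9.3.6 also omit loss to follow-up and removal by the Sponsor-Investigator, both of which section 7.4 makes discontinuation reasons. The lists can therefore be read as the general schedule and the hospice sentence as a specific exception. This stands in part. A reader might infer that the two rules are impossible to follow together; that is too strong. But reading 7.4 as an exception does not rescue the OS analysis, because it is exactly the reading under which the deaths are lost.

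A reader might also infer that section 3.3 is flatly contradicted. It is not: a maximum is not breached by stopping sooner, and its wording on record sources is permissive.

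The bias needs two steps that the documents do not state: that 7.4 is applied to passive collection of vital status, and that the analyst censors at hospice entry. Public records could still supply the deaths. This stands, and it is why the conclusion is conditional.

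Nor do the documents support reading the Cox comparison as tilted toward the trial. That would require historical deaths to have been counted regardless of hospice, and nothing is said about how they were ascertained.

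Finally, the figures rest on assumed rates and hazard shape, for an exploratory endpoint in a pilot that disclaims power for efficacy. That is correct. The calculation also credits the safety window over section 7.4, a ranking that the documents do not state. The direction of the bias depends on none of this.

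**Conclusion.** The point holds in conditional form. Section 7.4 stops follow-up at hospice entry where 8.1 footnote 6 and 9.3.6 continue it, and 10.1 has no censoring rule to decide between them. If 7.4 is followed and subjects are censored at hospice entry, Kaplan-Meier OS is biased upward.

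Confidence is high on the mismatch and the direction, and low on the size. About 1 to 6 points at 1 year is an illustration under the stated assumptions. It stays below one standard error with the day-132 window, but can exceed one with a shorter window or none, and it grows at later times.

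The primary necrosis endpoint and the secondary endpoints (RECIST response, adverse events) do not depend on how OS is censored. The amendment should be made because it is cheap. The gap between the 3-year duration and the 5-year estimates is a separate minor point and adds no weight to this one.

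**What to change.** 1. Section 7.4: limit the hospice sentence to on-study visits, and reconcile it with section 8.1 footnote 6 and section 9.3.6.
2. State that vital status and date of death are still collected after hospice entry, by the record route in section 3.3, unless the subject withdraws consent for this.
3. Section 10.1: define OS as time to death from any cause, censored at the date last known alive, and state that hospice entry is not a censoring event.
4. Section 10.1: ascertain deaths in the historical controls in the same way, or state the difference.
5. Separately, reconcile section 1.0 with section 10.1: restate the trial duration or drop the 5-year estimates.

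The cost is a wording amendment. No visits, sample size or primary analysis change, and record review is already foreseen. The sponsor must check that consent covers record review after hospice entry; the consent pages were not among the documents reviewed.
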